#### **4.4.18      Telephone Calls**

The purpose of this semi-structured interview is to identify new or worsening symptoms that warrant an unscheduled visit. The telephone interview is shown in [Appendix 3](#) and will be conducted after Visit 5 by site personnel familiar with the patient(s) every 12 weeks ( $\pm$  7 days) *after each study visit*.

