#### **4.4.19.2 Approval by the Institutional Review Board or Ethics Committee**

Collection and submission of biological samples to the RCR is contingent upon the review and approval of the exploratory research and the RCR portion of the Informed Consent Form by each site's Institutional Review Board or Ethics Committee (IRB/EC) and, if applicable, an appropriate regulatory body. If a site has not been granted approval for RCR sampling, this section of the protocol (Section [4.4.18](#)) will not be applicable at that site.

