### **5.3.1 Adverse Event Reporting Period**

Investigators will seek information on adverse events at each patient contact. All adverse events, whether reported by the patient or noted by study personnel, will be recorded in the patient's medical record and on the Adverse Event eCRF.

**After informed consent** has been obtained **but prior to initiation of study drug**, only serious adverse events caused by a protocol-mandated intervention (e.g., invasive procedures such as biopsies, discontinuation of medications) should be reported (see Section 5.4.2 for instructions for reporting serious adverse events).

**After initiation of study drug**, all adverse events will be reported until 28 days after the last dose of study drug. After this period, the investigator should report any serious adverse events that are believed to be related to prior study drug treatment (see Section 5.6).

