### **5.3.2 Eliciting Adverse Event Information**

A consistent methodology of non-directive questioning should be adopted for eliciting adverse event information at all patient evaluation timepoints. Examples of non-directive questions include the following:

"How have you felt since your last clinic visit?"

"Have you had any new or changed health problems since you were last here?"

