## **Appendix 3**

### **Telephone Interviews**

The following semi-structured telephone interview should occur after Visit 5, 12 weeks ( $\pm 7$  days) *after each study visit*. The purpose of this interview is to identify any new or worsening symptoms that warrant an unscheduled visit or reporting of an adverse event.

Please ask the following questions and record patient's answers during the Telephone Interview:

1. Since the last time we talked (at site or over the telephone), have you had any worsening medical problems? If yes, what were they?

---

---

2. Since your last visit or telephone interview, have you taken any new medicines? If yes, what were they?

---

---

3. Have you had problems or issues with the preparation or handling of the study drug?

---

---

If the patient answered YES to any question, contact the Treating Investigator and review the patient's answers. The Investigator can determine if an unscheduled visit is required.

Record any pertinent comments made by the patient during the interview:

---

---

NAME: \_\_\_\_\_ Date: \_\_\_\_\_

Name of person completing the telephone interview.

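### Question 1 of the Appendix 3 telephone script omits new symptoms, so a new event that is neither treated with a new medicine nor volunteered may not be referred at the call

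*Protocol*

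**What the plan says.** Section 4.4.18 gives the aim of the call, which covers symptoms that are either new or worsening: "The purpose of this semi-structured interview is to identify new or worsening symptoms that warrant an unscheduled visit". Appendix 3 goes further: "The purpose of this interview is to identify any new or worsening symptoms that warrant an unscheduled visit or reporting of an adverse event".

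The Appendix 3 script then has three questions:

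1. "Since the last time we talked (at site or over the telephone), have you had any worsening medical problems"
2. "Since your last visit or telephone interview, have you taken any new medicines"
3. A question on preparing or handling the study drug.

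A YES to any of the three means that the treating investigator is contacted and reviews the answers. The form also has space for comments from the patient, with no referral step attached to it.

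The general adverse event rules are wider than the script. Section 5.3.1 states: "Investigators will seek information on adverse events at each patient contact". Section 5.3.2 asks for consistent, non-directive questioning at every evaluation timepoint and gives as one example: "Have you had any new or changed health problems since you were last here".

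Section 3.1.1.3 and the Appendix 1 schedule place clinic visits 13 weeks apart up to Week 52 (Visit 5) and 26 weeks apart after that.

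**The concern.** The purpose statements name two targets, new symptoms and worsening symptoms. The only symptom question asks about the second. A patient whose problem began after the last contact, with nothing pre-existing made worse, can truthfully answer NO to Question 1.

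This matters because adverse events are the primary objective (Section 2.1), and after Visit 5 the call is the planned contact between clinic visits. If the call does not ask about new problems, those that arise soon after a visit wait for the next one. Longer recall puts short, minor, untreated events most at risk, and it makes onset dates less certain. Section 6.6 uses the onset date to assign each event to a dose.

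**Working it through.** The plan gives no figure for this point, so there is none to reproduce. The check has two parts.

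**Tracing a new event through the script**

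| Situation at the call | Q1 worsening | Q2 new medicine | Q3 handling | Investigator contacted by rule |
|---|---|---|---|---|
| Existing problem has worsened | YES | either | either | Yes |
| New event, treated with a new medicine | NO | YES | either | Yes |
| New event, no new medicine, handling problem | NO | NO | YES | Yes |
| New event, no new medicine, no handling problem | NO | NO | NO | No |

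The gap is the last row. It closes in practice if the patient volunteers the problem or the caller probes further, but the script requires neither.

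**Bounding the delay for events in that row**

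Inputs: visit interval 26 weeks (Appendix 1 schedule, after Visit 5); call at week 12 (Section 4.4.18 and Appendix 3). Assumptions: one call per interval, onsets spread evenly over the interval, and calls that catch none of these events as scripted and all of them after rewording.

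- Visits only: mean wait = 26/2 = 13.0 weeks; longest wait 26 weeks.
- Call at week 12 also asks: mean wait = (12²/2 + 14²/2)/26 = (72 + 98)/26 = 170/26 = 6.5 weeks; longest wait 14 weeks.
- Where the difference comes from: onsets before the call are 12/26 = 46% of the total, and each waits 14 weeks longer than it need, so 12 × 14/26 = 6.5 weeks averaged over all onsets. Onsets after week 12 are unaffected.

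Sensitivity:

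- The ±7-day call window hardly matters. At week 11 the mean is (11²/2 + 15²/2)/26 = 173/26 = 6.7 weeks; at week 13 it is (13²/2 + 13²/2)/26 = 169/26 = 6.5 weeks.
- If the calls run every 12 weeks, with calls at weeks 12 and 24, the mean wait with an asking call is (12²/2 + 12²/2 + 2²/2)/26 = 146/26 = 5.6 weeks.
- If calls already catch half of these events through probing or volunteered comments (an illustrative assumption), the present mean under the one-call reading is 13.0 − 0.5 × 6.5 = 9.75 weeks, about 9.8.

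**The case against.** The strongest reply is that the duty to ask already exists. A site call is a patient contact, so Section 5.3.1 applies to it. The interview is semi-structured and made by staff who know the patient, and Appendix 3 states the full aim at its head. Nothing confines the caller to the three questions. Section 4.4.15 provides for an unscheduled visit when a patient reports new symptoms, and the next clinic visit asks again. An event captured late can still be recorded with its true onset date and so assigned to the right dose.

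Most of this stands, and it limits the consequence: the usual result is late capture, not loss. It does not repair the script. Sections 5.3.1 and 5.3.2 show that the written question is narrower than the protocol's own method, and the unscheduled-visit route depends on the patient coming forward, which the call was meant to make less necessary.

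A reader might infer more than the documents support:

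- *That the call cannot detect a new event.* Question 2 picks up new events treated with a new medicine, and volunteered comments are recorded.
- *That most twice-daily exposure is affected.* The documents do not say how much of that exposure falls after Visit 5. Patients who increase their dose also have a dose increase visit and a safety follow-up visit 4 weeks later, both with adverse event collection and Holter monitoring.
- *That the first year used a broader question which was later dropped.* The Section 5.3.2 questions are examples for all evaluation timepoints, not a first-year script.
- *That sites without repository approval make no calls.* Section 4.4.19.2 does say "this section of the protocol (Section [4.4.18](#)) will not be applicable at that site", and Section 4.4.18 is Telephone Calls. In context this is plainly a numbering slip for the repository section, 4.4.19.

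**Conclusion.** The point holds in a narrow form. The script's symptom question contradicts the stated purpose of the call and the elicitation method in Section 5.3.2. New events that are neither treated with a new medicine nor volunteered may go unreferred at the call.

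For those events alone, the mean wait to the next enquiry is at most 13.0 weeks, against 6.5 weeks if a single week-12 call asked (5.6 weeks with a second call at week 24). This rests on evenly spread onsets and on calls that catch none of these events as scripted. It measures time to the next enquiry and does not count missed adverse events. The documents give no basis for estimating how many would be lost. The likely effect is delayed capture, with some loss of short, minor events. The change is still worth making, because it concerns the primary safety outcome and costs almost nothing.

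**What to change.** In Appendix 3, keep the opening of Question 1 (the period since the last contact, on site or by telephone) and replace its object, worsening medical problems, with the Section 5.3.2 object, new or changed health problems. In Section 4.4.18, add that any positive answer is assessed for adverse event recording under Section 5.3.1.

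The cost is a few words in one question and one added sentence, with no further contacts or staff. A small downside is that somewhat more non-serious adverse events may be recorded after the change, so the date of the new script should be kept in mind when event rates are compared over time.

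As editorial clean-up only:

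- Correct the cross-reference in Section 4.4.19.2 from 4.4.18 to 4.4.19.
- Reconcile the call timing. The telephone-call note to the Appendix 1 schedule has a repeating 12-week cycle after Visit 5, Appendix 3 has a call 12 weeks after each visit, and Section 4.4.18 combines the two. The first allows two calls in a 26-week interval and the second allows one.

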#### **4.4.19      Samples for Roche Clinical Repository**

##### **4.4.19.1      Overview of the Roche Clinical Repository**

The Roche Clinical Repository (RCR) is a centrally administered group of facilities used for the long-term storage of human biologic specimens, including body fluids, solid

tissues, and derivatives thereof (e.g., DNA, RNA, proteins, peptides). The collection and analysis of RCR specimens will facilitate the rational design of new pharmaceutical agents and the development of diagnostic tests, which may allow for individualized drug therapy for patients in the future.

Specimens for the RCR will be collected from patients who give specific consent to participate in this optional research. RCR specimens will be used to achieve the following objectives:

- To study the association of biomarkers with efficacy, adverse events, or disease progression
- To increase knowledge and understanding of disease biology
- To study drug response, including drug effects and the processes of drug absorption and disposition
- To develop biomarker or diagnostic assays and establish the performance characteristics of these assays

#### **4.4.19.2 Approval by the Institutional Review Board or Ethics Committee**

Collection and submission of biological samples to the RCR is contingent upon the review and approval of the exploratory research and the RCR portion of the Informed Consent Form by each site's Institutional Review Board or Ethics Committee (IRB/EC) and, if applicable, an appropriate regulatory body. If a site has not been granted approval for RCR sampling, this section of the protocol (Section [4.4.18](#)) will not be applicable at that site.

#### **4.4.19.3 Sample Collection**

The following samples will be collected from eligible patients who provide consent for research purposes, including but not limited to research on dynamic (non-inherited) biomarkers, and on genetic (inherited) biomarkers related to olesoxime, spinal muscular atrophy:

- DNA specimens for genetic biomarker (inherited) discovery and validation will be collected at baseline.  
**NB** If the sampling for DNA Specimens was missed during baseline, it may be collected in the next scheduled visit.
- Blood samples (collected in PAXgene vacutainers) will be collected for RNA analysis at timepoints specified in the Schedule of Assessments ([Appendix 1](#)).
- Blood for plasma isolation will be obtained at the timepoints indicated in the Schedule of Assessments ([Appendix 1](#)) for identification of dynamic (non-inherited) biomarkers.

These specimens will be used for research purposes and will help to better understand the pathogenesis, course, and outcome of SMA and related diseases. For all samples, dates of consent should be recorded on the associated RCR page of the eCRF. For

sampling procedures, storage conditions, and shipment instructions, see the laboratory manual.

RCR specimens will be destroyed no later than 15 years after the date of final *clinical study report*. The RCR storage period will be in accordance with the IRB/EC-approved Informed Consent Form and applicable laws (e.g., health authority requirements).

The dynamic biomarker specimens (RNA, plasma) will be subject to the confidentiality standards described in Section 8.4. The genetic biomarker specimens will undergo additional processes to ensure confidentiality, as described below.

#### **4.4.19.4      Confidentiality**

Given the sensitive nature of genetic data, Roche has implemented additional processes to ensure patient confidentiality for RCR specimens and associated data. Upon receipt by the RCR, each specimen is "double-coded" by replacing the patient identification number with a new independent number. Data generated from the use of these specimens and all clinical data transferred from the clinical database and considered relevant are also labeled with this same independent number. A "linking key" between the patient identification number and this new independent number is stored in a secure database system. Access to the linking key is restricted to authorized individuals and is monitored by audit trail. Legitimate operational reasons for accessing the linking key are documented in a standard operating procedure. Access to the linking key for any other reason requires written approval from the Pharma Repository Governance Committee and Roche's Legal Department, as applicable.

Data generated from RCR specimens must be available for inspection upon request by representatives of national and local health authorities, and Roche monitors, representatives, and collaborators, as appropriate.

Patient medical information associated with RCR specimens is confidential and may be disclosed to third parties only as permitted by the Informed Consent Form (or separate authorization for use and disclosure of personal health information) signed by the patient and/or legal guardian, unless permitted or required by law.

Data derived from RCR specimen analysis on individual patients will generally not be provided to study investigators unless a request for research use is granted. The aggregate results of any research conducted using RCR specimens will be available in accordance with the effective Roche policy on study data publication.

Any inventions and resulting patents, improvements, and/or know-how originating from the use of the RCR data will become and remain the exclusive and unburdened property of Roche, except where agreed otherwise.

#### **4.4.19.5 Consent to Participate in the Roche Clinical Repository**

The Informed Consent Form will contain a separate section that addresses participation in the RCR. The investigator or authorized designee will explain to each patient and/or legal guardian the objectives, methods, and potential hazards of participation in the RCR. Patients and/or legal guardians will be told that they are free to refuse to participate and may withdraw their specimens at any time and for any reason during the storage period. A separate, specific signature will be required to document a patient's and/or legal guardian's agreement to provide optional RCR specimens. Patients who decline to participate will not provide a separate signature.

The investigator should document whether or not the patient has given consent to participate by completing the RCR Research Sample Informed Consent eCRF.

In the event of an RCR participant's death or loss of competence, the participant's specimens and data will continue to be used as part of the RCR research.

#### **4.4.19.6 Withdrawal from the Roche Clinical Repository**

Patients and/or legal guardians who give consent to provide RCR specimens have the right to withdraw the specimens from the RCR at any time for any reason. If a patient and/or legal guardian wishes to withdraw consent to the testing of his or her specimens, the investigator must inform the Medical Monitor in writing of the patient's wishes through use of the RCR Subject Withdrawal Form and, if the trial is ongoing, must enter the date of withdrawal on the RCR Research Sample Withdrawal of Informed Consent eCRF. The patient will be provided with instructions on how to withdraw consent after the trial is closed. A patient's withdrawal from Study BN29854 does not, by itself, constitute withdrawal of specimens from the RCR. Likewise, a patient's withdrawal from the RCR does not constitute withdrawal from Study BN29854.

#### **4.4.19.7 Monitoring and Oversight**

RCR specimens will be tracked in a manner consistent with Good Clinical Practice by a quality-controlled, auditable, and appropriately validated laboratory information management system, to ensure compliance with data confidentiality as well as adherence to authorized use of specimens as specified in this protocol and in the Informed Consent Form. Roche monitors and auditors will have direct access to appropriate parts of records relating to patient participation in the RCR for the purposes of verifying the data provided to Roche. The site will permit monitoring, audits, Institutional Review Board/Ethics Committee (IRB/EC) review, and health authority inspections by providing direct access to source data and documents related to the RCR samples.

## **4.5 PATIENT, TREATMENT, STUDY, AND SITE DISCONTINUATION**

### **4.5.1 Patient Discontinuation**

Patients have the right to voluntarily withdraw from the study at any time for any reason. In addition, the investigator has the right to withdraw a patient from the study at any time. Reasons for withdrawal from the study may include, but are not limited to, the following:

- Patient withdrawal of consent at any time
- Any medical condition that the investigator or Sponsor determines may jeopardize the patient's safety if he or she continues in the study
- Investigator or Sponsor determines it is in the best interest of the patient

Every effort should be made to obtain information on patients who withdraw from the study. The primary reason for withdrawal from the study should be documented on the appropriate eCRF. However, patients will not be followed for any reason after consent has been withdrawn (*except for safety follow-up, as described in Section 3.1.1.5*).

Patients who withdraw from the study will not be replaced.

### **4.5.2 Study Treatment Discontinuation**

Patients must discontinue study treatment if they experience any of the following:

- Ongoing pregnancy

The primary reason for study treatment discontinuation should be documented on the appropriate eCRF. Patients should be invited to the site to perform a Study Discontinuation Visit. Patients who discontinue study treatment prematurely will not be replaced.

### **4.5.3 Study and Site Discontinuation**

The Sponsor has the right to terminate this study at any time. Reasons for terminating the study may include, but are not limited to, the following:

- The incidence or severity of adverse events in this or other studies indicates a potential health hazard to patients.

The Sponsor will notify the investigator if the Sponsor decides to discontinue the study.

The Sponsor has the right to close a site at any time. Reasons for closing a site may include, but are not limited to, the following:

- Poor protocol adherence
- Inaccurate or incomplete data recording
- Non-compliance with the ICH guideline for Good Clinical Practice
- No study activity (i.e., all patients have completed and all obligations have been fulfilled)

## **5. ASSESSMENT OF SAFETY**

### **5.1 SAFETY PLAN**

Olesoxime is not approved and is currently in clinical development. Thus, the entire safety profile is not known at this time. Based on clinical experience to date there are no identified risks with olesoxime (for additional information please refer to the Olesoxime Investigator's Brochure). The safety plan for this study is designed to ensure patient safety and will include specific eligibility criteria (Section 4.1.2 and Section 4.1.3) and monitoring for adverse events and other safety parameters as described in the Schedule of Assessments ([Appendix 1](#)).

### **5.2 SAFETY PARAMETERS AND DEFINITIONS**

Safety assessments will consist of monitoring and recording adverse events, including serious adverse events and adverse events of special interest, performing protocol-specified safety laboratory assessments, measuring protocol-specified vital signs, and conducting other protocol-specified tests that are deemed critical to the safety evaluation of the study.

Certain types of events require immediate reporting to the Sponsor, as outlined in Sections [5.2.2](#) and [5.2.3](#).

#### **5.2.1 Adverse Events**

According to the ICH guideline for Good Clinical Practice, an adverse event is any untoward medical occurrence in a clinical investigation subject administered a pharmaceutical product, regardless of causal attribution. An adverse event can therefore be any of the following:

- Any unfavorable and unintended sign (including an abnormal laboratory finding), symptom, or disease temporally associated with the use of a medicinal product, whether or not considered related to the medicinal product
- Recurrence of an intermittent medical condition (e.g., headache) not present at baseline
- Any deterioration in a laboratory value or other clinical test (e.g., ECG, X-ray) that is associated with symptoms or leads to a change in study treatment or concomitant treatment or discontinuation from study drug
- Adverse events that are related to a protocol-mandated intervention, including those that occur prior to assignment of study treatment (e.g., screening invasive procedures such as blood draw).

